7.2 Exploratory endpoints

Exploratory endpoints include

- Change from Baseline in Diabetic Retinopathy Severity Scale (DRSS) score at Weeks 24 and 48
- Change in capillary perfusion from Baseline to Weeks 12, 24, and 48 as assessed by Optical Coherence Tomography Angiography (OCT-A) and Fluorescein Angiography (FA)

Change from Baseline in DRSS score will be presented as the proportion of patients with a \geq 2step improvement in diabetic retinopathy (DR) severity from baseline on the ETDRS DRSS at Weeks 24 and 48. The proportion of patients with a \geq 2-step improvement in diabetic retinopathy (DR) severity from baseline will be analyzed using the analysis method following those for the binary secondary efficacy endpoints.

For change in capillary perfusion from Baseline to Weeks 12, 24, and 48, the analysis method will follow those for the continuous secondary efficacy endpoints.

Key parameters of OCT-A and FA will be summarized, and all OCT-A, FA and CFP data will be listed.

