study, the Sponsor expects systemic exposure of UBX1325 following IVT treatment to be low in patients and, therefore, the potential to observe such systemic events is also low.
Tier	Objective	Endpoints
Primary	Assess the local and systemic safety and tolerability following a single-dose IVT injection of UBX1325 in patients with DME	• Ocular and systemic safety and tolerability of a single IVT injection of UBX1325 evaluated by treatment emergent adverse events (TEAEs)
Secondary	Assess the biological activity following a single UBX1325 injection in patients with DME Assess further efficacy parameters and retinal structure improvement of patients following a single UBX1325 injection compared to sham	 Changes in BCVA from Baseline to Weeks 12, 24 and 48 Proportion of patients who require 2 or more anti-VEGF rescue over 12, 24 and 48 Weeks Change in CST from Baseline to each study visit as assessed by SD-OCT and read by a Reading Center Change in CST area under the curve (AUC) from baseline to each study visit Proportion of patients without macular fluid at Weeks 12, 24 and 48 as assessed by SD-OCT
Exploratory	Assess further efficacy parameters and retinal structure improvement of patients followinga single UBX1325 injection compared to sham	 Change from Baseline in Diabetic Retinopathy Severity Scale (DRSS) score at Weeks 24 and 48 Change in capillary perfusion from Baseline to Weeks 12, 24 and 48 as assessed by OCT-A and FA

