8.5 Efficacy Analysis

The Full Analysis Set will be used for all efficacy analyses.

The BCVA will be assessed using the ETDRS chart starting at 4 meters at each study visit. Change in BCVA from baseline to each visit will be analyzed by mixed model for repeated measures (MMRM). The details of MMRM and the analysis methods for other efficacy endpoints described in Section 3 will be provided in the SAP.

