3.1 General considerations

All study parameters will be listed, and a selected list of parameters will be summarized descriptively by study arm and overall. The descriptive statistics will include number of subjects, mean, standard deviation, median, minimum, and maximum for continuous parameters, and frequency and percent for categorical parameters.

The following reporting conventions will be implemented:

- All statistical tests will be conducted as 2-sided tests unless otherwise specified.
- Confidence intervals (CIs) will be presented as 2-sided 95% CIs unless otherwise specified.
- All mean and median values will be formatted to one more decimal place than the measured value. Standard deviation values will be formatted to two more decimal places than the measured value.
- All percentages will be rounded to one decimal place. The number and percentage of responses will be presented in the form xx (xx.x), where the percentage is in the parentheses. The percentage will be omitted when the numerator is zero. In the case the numerator is equal to the denominator, the percentage should be presented as (100) instead of (100.0).
- All analysis and summary tables will have the analysis population sample size (*i.e.*, number of participants) wherever applicable.

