Proportion of patients who require 2 or more, or 1 or more anti-VEGF rescue over 12, 24, and 48 Weeks will be summarized for each treatment group. Confidence intervals of difference in proportions between treatment groups will be calculated using an exact method (Chan and Zhang, 1999) implemented in the SAS procedure Freq. Criteria for rescue therapy are worsening of CST by 75 μ m relative to Baseline and/or a 10-letter decrease in BCVA compared to peak BCVA from Baseline. Patients who meet rescue criteria can be rescued with anti-VEGF treatment. Rescued patients will continue with study visits per protocol. Proportion of patients without macular fluid at Weeks 12, 24, and 48 as assessed by SD-OCT will be analyzed using same method.

BCVA and SD-OCT data will be listed.

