9.2 File management and data security

Data and program files will be managed according to BSSI SOP-OP-002, Folder and File Structure Management. Electronic file security and integrity will be protected by procedures outlined in BSSI SOP-IT-002, Data Security.

10. Changes in the Statistical Analysis Plan from the Protocol Analysis Plan

The definition of the Full Analysis Set has changed from the protocol to be based on BCVA instead of CST. The area under the curve (AUC) of change from baseline of BCVA for each study visit has been added as a secondary efficacy endpoint.

11. References

AAO PPP DME Guidelines (2019) available at https://www.aaojournal.org/article/S0161-6420(19)32092-5/pdf

Chan, I. S. F., and Zhang, Z. (1999). Test-Based Exact Confidence Intervals for the Difference of Two Binomial Proportions. *Biometrics* 55:1202–1209.

Coney JM. (2019) Addressing unmet needs in diabetic retinopathy. *American Journal of Managed Care* 25:S0.

12. Appendices

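### SAP 7.2 reduces change in DRSS score to a 2-step improvement rate, so no planned between-arm summary shows one-step changes or any worsening

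*SAP*

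**What the plan says.** Protocol Section 3 lists the exploratory endpoint as "Change from Baseline in Diabetic Retinopathy Severity Scale (DRSS) score at Weeks 24 and 48", and SAP 1.3.3 repeats it. Neither place gives a step size, a direction or a summary measure.

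Protocol 8.5 specifies a repeated-measures model for BCVA and leaves the rest open: "The details of MMRM and the analysis methods for other efficacy endpoints described in Section 3 will be provided in the SAP".

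SAP 7.2 fills the gap. "Change from Baseline in DRSS score will be presented as the proportion of patients" with an improvement of two or more steps, and this proportion "will be analyzed using the analysis method following those for the binary secondary efficacy endpoints". For those endpoints SAP 7.1 gives a summary by group and an interval: "Confidence intervals of difference in proportions between treatment groups will be calculated using an exact method (Chan and Zhang, 1999"). SAP 3.1 sets two-sided 95% as the default level.

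SAP 3.1 also has a general rule: "All study parameters will be listed, and a selected list of parameters will be summarized descriptively by study arm and overall". The listing sentence in SAP 7.2 names OCT-A, FA and CFP but not DRSS. SAP Section 8 (safety) contains no DRSS summary.

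**The concern.** The endpoint is a change on an ordered scale and can go either way. The planned summary has two classes: improved by at least two steps, and everyone else. The second class mixes one-step improvement, no change, one-step worsening and any larger worsening.

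This matters because of the sponsor's own reasoning. Protocol 2.3.1 says that removing senescent cells might slow disease progression, and mentions recovery as a further possibility. Slowed progression would appear as less worsening on active than on sham. No planned comparison of the arms can show that pattern, or its opposite. A proof-of-concept trial uses such an endpoint to learn the direction and size of change, and here the plan reports only one tail.

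**Working it through.** **1. The plan's own figure.** The only sizing in the documents is for BCVA: difference 8, SD 13, two-sided 0.15, power 80%, dropout 5%.

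- n per arm = 2(1.4395 + 0.8416)² × 13²/8² = 2 × 5.204 × 2.641 = 27.5, so 28.
- 28/0.95 = 29.5, so 30 per arm and 60 in total, against 62 stated. The figure reproduces within two patients.
- 31 × 0.95 = 29.45, so about 29 evaluable per arm. That number is used below. The documents size nothing for DRSS.

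**2. What each class contains.** The documents give no DRSS rates or SD. Assume that step change on sham is a rounded normal with mean 0 and SD 1.0.

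| Step change (sham) | Probability | Expected of 29 | Class in SAP 7.2 |
|---|---|---|---|
| 2 or more better | 1 − Φ(1.5) = 0.067 | 1.9 | responder |
| 1 better | Φ(1.5) − Φ(0.5) = 0.242 | 7.0 | other |
| 0 | 2Φ(0.5) − 1 = 0.383 | 11.1 | other |
| 1 worse | 0.242 | 7.0 | other |
| 2 or more worse | 0.067 | 1.9 | other |

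Suppose treatment turned every worsening into no change and did nothing else. The responder rate would stay at 1.9 against 1.9 of 29. The step distribution would show about 9 worsened on sham (7.0 + 1.9) against none on active. The true difference in responder rate is zero, so any significant result is a false positive. Simulated rejection at the 0.15 level was 0 to 12% over the assumed prevention-only settings, below the nominal 15%.

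**3. Information kept by the 2-step cut.** For a uniform shift of a normal change, a cut with upper-tail probability p at standard normal point c keeps φ(c)²/[p(1 − p)] of the information. At p = 0.10, c = 1.282 and φ(c) = 0.1755, giving 0.0308/0.09 = 34% of a continuous measure, or 36% of the integer-step scale. Relative to integer steps:

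| Assumed 2-step improvement rate | Improvement rate alone | With a 2-step worsening class added |
|---|---|---|
| 5% | 24% | 46% |
| 10% | 36% | 65% |
| 15% | 44% | 75% |
| 20% | 50% | 80% |
| 25% | 55% | 82% |

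**4. Is an ordered test better?** Power at 29 per arm, two-sided 0.15, mean benefit 0.5 step in both scenarios, rank test against a pooled z-test on the 2-step improvement rate:

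| SD | Every patient shifts 0.5 step | 25% gain 2 steps, the rest none |
|---|---|---|
| 0.8 | 77% v 33% | 54% v 77% |
| 1.0 | 65% v 37% | 46% v 59% |
| 1.3 | 48% v 33% | 39% v 44% |

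A repeat of the SD 1.0 cell on the right gave 48% v 62%. The ranking reverses with the shape of the effect, and the documents do not say which shape to expect. These runs use a z-test at 0.15, which is the BCVA sizing level. The SAP plans exact 95% intervals for DRSS, so the figures are illustrative only.

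**The case against.** A reader might infer that the SAP silently departed from the protocol. The documents do not support that. The protocol fixed no DRSS analysis, Protocol 8.5 handed the method to the SAP, and the SAP keeps the endpoint wording and weeks. SAP Section 10 records changes of another kind: a definition that the protocol had stated ("The definition of the Full Analysis Set has changed from the protocol to be based on BCVA instead of CST") and a new measure, the AUC of BCVA, that "has been added as a secondary efficacy endpoint". With no protocol analysis of DRSS there was nothing to declare.

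A reader might also infer that most of the information is thrown away, or that an ordered test would clearly be more powerful. The first is true only under an assumed shift model and a responder rate below about 20%. The second fails when a minority of patients respond strongly.

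Nor is harm invisible. Safety rests on treatment-emergent adverse events, including ocular events in the study eye (SAP 8.1). Individual DRSS values fall under the general listing rule, and Protocol 8.6.1 allows further exploratory analyses. Table specifications are in a separate document not available here, so a step table may already be intended.

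All of this stands, and it limits the point. It does not answer it. Listings and adverse events do not compare DRSS worsening between arms, and a permission for later analyses is not a commitment to this one.

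**Conclusion.** The point holds as a cheap improvement. SAP 7.2 gives a narrow definition of a loosely worded endpoint, and one-step changes and all worsening are absent from every planned between-arm summary of DRSS. The blindness to a prevention-only effect follows from the definition and needs no assumption. Its size does: the 0 to 12% rejection rate and the information figures rest on assumed rounded-normal step changes and about 29 evaluable patients per arm.

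The weight is low. The endpoint is exploratory, carries no power claim, and no multiplicity adjustment depends on it. The material supports neither a charge of an undisclosed protocol change nor a general claim that a rank test should replace the responder rate.

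**What to change.** In SAP 7.2:

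- Keep the rate of improvement by two or more steps.
- Add, at Weeks 24 and 48, the distribution of DRSS step change by arm. This also shows one-step changes, which a 2-step worsening rate alone would miss.
- Add the rate of worsening by two or more steps, with the same exact confidence interval for the difference.
- Optionally, add an ordered test stratified by the randomisation factor (most recent anti-VEGF agent), labelled descriptive, because its power relative to the responder rate depends on the unknown shape of the effect.

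DRSS scores at these visits are already in the schedule of events, so no new data are needed. The cost is one extra exploratory table and a further result to interpret on an endpoint with no error control.

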7.3 Subgroup Analyses

The following subgroups will be analyzed with respect to two secondary efficacy endpoints: change in BCVA from Baseline to Weeks 12, 24, and 48, and change in CST from Baseline to each study visit.

- Baseline BCVA (≤60 letters and >60 letters)
- Baseline CST (\leq 400 µm and >400 µm)
- Baseline DR severity (<47, ≥47 DRSS score)
- Baseline HbA1c (≤7% and >7%)

The analysis method will be the same as specified above for each respective endpoint. The subgroup categories may be adjusted if there is not enough representation of a specific subpopulation or treatment group. Additional analysis of BCVA and CST with the subgroup as covariate may be performed if clinically significant subgroup difference is observed in the subgroup analysis.

8. Safety Analysis

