2.4 Determination of sample size

Assuming the difference of change from Baseline in BCVA between UBX1325 and sham is 8 letters, the standard deviation is 13 letters, and the drop-out rate is 5%, a sample size of 62 subjects (31 per group) would provide 80% power to detect the difference at a two-sided significance level of 0.15.

3. General Methods

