7.1 Secondary endpoints

The following continuous secondary efficacy endpoints will be analyzed using mixed models for repeated measures (MMRM):

- Change in BCVA from Baseline to Weeks 12, 24, and 48
- Change in CST from Baseline to each study visit as assessed by SD-OCT and read by a Reading Center
- Area under the curve (AUC) of change from baseline of CST for each study visit
- Area under the curve (AUC) of change from baseline of BCVA for each study visit

The MMRM will be used for the primary analysis of the change from baseline in BCVA, which is based on the ETDRS VA chart assessed at a starting distance of four meters. The model will include the change from baseline at Day 2, Week 1 to Week 48 as the dependent variable, and the independent variables will include continuous BCVA baseline, categorical treatment arm

(active or sham), categorical study visit, and arm-by-visit interaction. Within-subject correlation will be modeled using subject-specific random intercepts. The model will assume a compound symmetry covariance structure. If there are convergence problems with this model, then other covariance structure may be fitted. The primary analysis will be limited to data collected prior to or on the rescue date. A supportive analysis will be performed for all data collected, regardless of rescue therapy. Subjects who violated major inclusion or exclusion criteria will be excluded from the primary and supportive analyses.

When BCVA outliers occur, a sensitivity analysis excluding the outliers will be performed. If deemed appropriate, other sensitivity analyses may also be considered to assess the impact of outliers.

The change from baseline in CST, as assessed by SD-OCT and read by a Reading Center, AUC of change from baseline in BCVA and CST, will be analyzed using MMRM, same as the analysis of BCVA.

The following binary secondary efficacy endpoints will be summarized:

- Proportion of patients who require 2 or more, or 1 or more anti-VEGF rescue over 12, 24, and 48 Weeks
- Proportion of patients without macular fluid at Weeks 12, 24, and 48 as assessed by SD-OCT

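### The follow-up to an apparent subgroup difference (SAP 7.3) names the subgroup only as a covariate; no treatment-by-subgroup term is planned to estimate a difference in treatment effect.

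*SAP*

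**What the plan says.** SAP 7.3 lists four two-level baseline factors: BCVA, CST, DR severity and HbA1c. The outcomes are "change in BCVA from Baseline to Weeks 12, 24, and 48, and change in CST from Baseline to each study visit". On method it says "The analysis method will be the same as specified above for each respective endpoint", which I read as the main MMRM run separately within each subgroup. It then adds that a further analysis of the two outcomes "with the subgroup as covariate may be performed if clinically significant subgroup difference is observed".

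The MMRM in SAP 7.1 has baseline value, treatment arm, "categorical study visit, and arm-by-visit interaction". That is the only interaction named in the SAP. SAP 7.3 sets no threshold for a clinically significant difference and lets the subgroup categories be changed if a group is thinly represented. SAP 3.7 plans no multiplicity adjustment. The protocol has no subgroup plan; its section 8.5 leaves the MMRM details to the SAP.

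**The concern.** The follow-up is prompted by a difference between subgroups. If that is a difference in treatment effect, the quantity wanted is the treatment-by-subgroup interaction. A covariate main effect shifts both arms of a subgroup by the same amount and leaves a single treatment effect for everyone, so the model cannot describe what prompted it.

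For one factor it would also add little. Continuous baseline BCVA is already in the BCVA model, so a 60-letter cut of the same variable is nearly redundant there.

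What is at stake is interpretation. Each subgroup holds about 15 patients per arm under an even split, so subgroup estimates will often look different by chance. The plan gives no direct estimate of the difference, with its uncertainty, to set beside that impression.

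**Working it through.** **Inputs.** From SAP 2.4 (identical in protocol 8.2): difference 8 letters, SD 13, dropout 5%, 31 per arm, 80% power, two-sided alpha 0.15. Not in the documents, so assumed: subgroup shares, the residual SD after baseline adjustment, and the size of a clinically significant subgroup difference, for which I use 8 letters.

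**1. The plan's own figure.** Normal approximation: n per arm = 2 × (1.44 + 0.84)² × 13² / 8², which rounds up to 28. With the noncentral t, 28 per arm gives 79.99% power and 29 gives 81.1%. Then 29 / 0.95 = 30.5, rounded up to 31 per arm, or 62 in total. The stated size reproduces.

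**2. What the covariate model returns.** Take a true effect of 8 letters in one subgroup and 0 in the other, with equal subgroup sizes.
- Arm + subgroup: one treatment effect of (8 + 0)/2 = 4 letters and a subgroup main effect of 4. The difference in effect does not appear.
- Arm + subgroup + arm-by-subgroup: interaction of 8 letters.

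This result depends on no variance assumption.

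**3. Size of chance differences, one factor, one visit.** Evaluable per arm: 31 × 0.95 = 29.45. With a 50/50 split, each subgroup has 14.7 per arm.
- SE of one subgroup effect = 13 × √(2/14.7) = 4.8 letters
- SE of the difference between two subgroup effects = 4.8 × √2 = 6.8 letters (6.78 unrounded)
- P(absolute difference ≥ 8, no true heterogeneity) = 2 × [1 − Φ(8/6.78)] = 0.238

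**4. At least one of four factors, treated as independent.** 1 − (1 − 0.238)⁴ = 0.66.

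**5. Sensitivity (29.45 per arm).**

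| SD | Split | SE of difference | One factor | At least one of four |
|---|---|---|---|---|
| 13 | 50/50 | 6.78 | 24% | 66% |
| 13 | 70/30 | 7.39 | 28% | 73% |
| 13 | 80/20 | 8.47 | 35% | 82% |
| 11 | 50/50 | 5.73 | 16% | 51% |
| 10 | 50/50 | 5.21 | 12% | 41% |

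The four factors are unlikely to be independent. Simulation with 29 per arm, SD 13 and an even split gives 62–68% at one visit for latent factor correlations of 0 to 0.6. Looking across Weeks 12, 24 and 48, with assumed within-patient correlation of 0.5–0.7, it gives about 88–95%. Restricting the primary analysis to data up to rescue (SAP 7.1) would leave fewer patients at later visits and raise the SD 13 figures.

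**6. What an interaction term would deliver.** At SD 13 and 50/50, the 95% half-width is 1.96 × 6.78 = 13.3 letters. Power for a true 8-letter interaction is about 40% at two-sided 0.15 and 22% at 0.05. For 80% power at 0.15, the SE formula implies four times the main-effect size: 4 × 2 × 28 = 224 evaluable patients.

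**The case against.** **The purpose is not stated.** SAP 7.3 calls the model an additional analysis that may be done; it does not say that it tests heterogeneity. The trigger could mean a prognostic difference, for which a covariate is the usual adjustment, and the word covariate does not strictly exclude an interaction. This stands: the text does not support reading the sentence as a definite main-effect-only test of effect modification. The criticism is conditional on the trigger meaning a difference in treatment effect. Even so, the sentence needs to say which is meant.

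**Much of the information is already planned.** Separate fits with the default 95% intervals (SAP 3.1) permit informal comparison. The subgroups are disjoint, so the interaction and its SE can be approximated from them. Protocol 8.6.1 also allows further exploratory analyses. This stands too, but the comparison is left to the reader, and an interaction analysis is permitted without being specified.

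**The percentages do not measure harm from the sentence.** Correct. They describe noise in the first-step subgroup estimates and would be the same without it. They show only why the difference should be reported with its uncertainty.

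**The remedy is imprecise.** Also correct. A reader might infer that an interaction term would separate chance from real effect modification; at ±13 letters it would not do so reliably. A reader might also infer that a false responder subgroup would shape the next trial, but neither document ties these four factors to later patient selection.

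**Conclusion.** If the trigger is a difference in treatment effect, the follow-up as worded cannot estimate it, and no other planned model term does. That conclusion is structural and rests on no numerical assumption.

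The size figures rest on the planning SD, an assumed even split, one visit, and 8 letters as a stand-in trigger. It would overstate them to call a chance difference of that size likely for any given factor: at one visit it is about one in four (12–35% over the range shown). It is more likely than not only for at least one of the four factors, and at an SD of 10–11 that falls to about even or a little below.

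Severity is minor to moderate. These are subgroup analyses of secondary endpoints in a phase 2a trial whose primary endpoint is safety, and no primary conclusion depends on them.

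**What to change.** Replace the last sentence of SAP 7.3 with:

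> For each of the four factors, regardless of the observed subgroup results, the MMRM will add subgroup, subgroup-by-visit, treatment-by-subgroup and treatment-by-subgroup-by-visit terms. The difference in treatment effect between subgroups, with its CI, will be reported at Weeks 12, 24 and 48 for BCVA and at each study visit for CST, and labelled exploratory.

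The subgroup-by-visit term is needed so that a purely prognostic time pattern is not picked up by the three-way term. If prognostic adjustment was also intended, state it as a separate analysis.

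The cost is SAP wording and a larger model. BCVA has 11 post-baseline visits in the schedule of events, so the fixed effects rise from 23 (intercept, baseline, arm, 10 visit, 10 arm-by-visit) by 22 (1 + 10 + 1 + 10) to 45. The confidence intervals will be wide, and the report should say that this is not a powered test.
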